**A Pilot Study to Evaluate the Feasibility and Potential
Effectiveness of the Flexitouch® System Head and Neck
Treatment**

Protocol# 4030

September 26, 2017

Protocol Version 2.0

[name], RN, Vanderbilt University School of Nursing (Principal Investigator)
[name], Co-I (Oncologist) [name], Co-I (Biostatistics)

Investigator Signature

Protocol Title: A Pilot Study to Evaluate the Feasibility and Potential Effectiveness of the Flexitouch® System Head and Neck Treatment

Protocol Number: 4030
Version: 2.0; 26 September 2017

I confirm that I have read this protocol. I will comply with the protocol and the principles of Good Clinical Practices (GCP), the International Conference on Harmonization Guidelines, Therapeutic Goods Act, institutional research policies and procedures and other appropriate regulatory requirements.

Site Principal Investigator Name (Print)

Site Principal Investigator Signature

Date

SYNOPSIS

Title of Study	A Pilot Study to Evaluate the Feasibility and Potential Effectiveness of the Flexitouch® System Head and Neck Treatment
Protocol Date	26 September 2017
Protocol Version	2.0
Name of Sponsor	Tactile Medical™
Investigational Product	Flexitouch® System Head and Neck System
Primary Aim	To determine the feasibility of use of the Flexitouch® Head and Neck System, specifically a) to evaluate implementation fidelity (adherence) and barriers to implementation fidelity, b) to establish safety, and c) to assess satisfaction.
Secondary Aim	To determine the preliminary efficacy of the Flexitouch® Head and Neck System compared to a wait-list control for the following outcomes: a) reduction in swelling/inflammation, b) function (cervical, jaw, and shoulder range of motion), c) symptoms, and d) quality of life changes.
Primary Endpoint	The primary endpoint will occur when subjects complete the 8th week of interventional treatment and provide: a) evaluation of implementation fidelity (adherence) and barriers to implementation fidelity, b) review of adverse events, and c) report satisfaction.
Secondary Endpoint	The secondary endpoint will occur at the same time as the primary endpoint. Secondary outcomes include: a) reduction in swelling/inflammation, b) function (cervical, jaw and shoulder range of motion), c) symptoms, and d) quality of life.
METHODOLOGY	
Study Design	This study is an open label, multi-site, stratified randomized, wait list control, pilot study.
Treatments	Standard home care may include: self-MLD, exercise, skin care, and wearing an appropriate compression garment, if applicable. Interventional treatment: twice daily treatment with Flexitouch® pneumatic compression device and home care regimen, which may include self-MLD exercise, skin care, and wearing an appropriate compression garment, if applicable.
Treatment Duration	The interventional study duration is 8 weeks. The subjects randomized to the investigational group will be seen at baseline and weeks 1, 4 and 8. Subjects randomized to the wait-list group will be seen at baseline and weeks, 1, 4 and 8 while receiving standard of care (SOC) treatment (wait-list control group).
SUBJECT POPULATION	
Number Planned	40 subjects randomized with replacement of up to 10 early withdrawals.


Major Inclusion/Exclusion Criteria
	
Inclusion Criteria :
 
 • Age ≥ 18 years • A previous diagnosis of histologically defined head and neck cancer • A diagnosis of head and neck lymphedema • Must be able and willing to participate in all aspects of the study and provide informed consent prior to study participation • Completed cancer treatment with no evidence of active cancer; all post-surgical swelling must be resolved. • The head and neck garments must fit appropriately. For patients with a tracheostomy, the fit will be assessed to ensure that the garments do not interfere with their tracheostomy. • The subject must have experienced at least one of the following: 
 ○ Completion of phase 1 lymphedema care in the past 8 weeks ○ The inability to participate/complete phase 1 care due to: 
 ▪ lack of available therapist/clinic ▪ lack of insurance coverage/funding to support cost of care. 
Exclusion Criteria :
 
 • Uncontrolled hyperthyroidism or parathyroidism (for which endocrinologist recommends against neck compression) • Carotid sinus hypersensitivity syndrome • Symptomatic carotid artery disease, as manifested by a recent transient ischemic attack (within 30 days), ischemic stroke, or amaurosis fugax (monocular visual ischemic symptoms or blindness) • Symptomatic bradycardia in the absence of a pacemaker • Internal jugular venous thrombosis, acute or within 3 months • Increased intracranial pressure or other contraindications to internal or external jugular venous compression • Acute radiation dermatitis, unhealed surgical scar, unhealed or open wound(s), surgical flap less than 6-8 week post-operative • Facial or head and neck dermal metastasis • Acute facial infection (e.g., facial or parotid gland abscess) • Any condition in which increased venous and lymphatic return is undesirable • History of pulmonary edema or decompensated congestive heart failure with in six (6) week of enrollment. • Subject is pregnant or trying to become pregnant

ASSESSMENTS
	

Feasibility /Safety
	
Adherence and barriers monitoring Adverse Event Monitoring (CTCAE) Satisfaction-Subject Self-report Physical Examination

Efficacy	
Visits will take place at Vanderbilt University School of Nursing, Vanderbilt Medical Center, or other facility approved location. Any additional sites will see patients in a location as determined by their research environment. Home visits may take place if unexpected circumstances arise that compromise data collection taking place in a timely manner. The following assessments will be completed at predefined times throughout the study.
 
• Digital Photos• Endoscopy / Revised Patterson Scale• Cytokine testing• Neck Disability Index• Voice Handicap Index• Range of Motion Measures
○ Cervical ROM○ Jaw ROM○ Shoulder ROM• Vanderbilt Head and Neck Symptom Survey• Lymphedema Symptom Intensity and Distress Survey• Linear Analog Self-Assessment Quality of Life
-----------------	---

TABLE OF CONTENTS

1.1	Contact Information	8
1.2	Sponsor Contact Information.....	8
1.3	Study Principal Investigator Information.....	8
2.0	Abbreviations	8
3.1	Introduction.....	9
3.2	Background and Rationale.....	9
3.3	Device Description	10
4.1	Study Objectives	10
4.2	Objective.....	10
4.3	Primary Aim	10
4.4	Secondary Aim	10
5.1	Study Design.....	10
5.2	Study Endpoints.....	11
5.2.1	Primary Endpoint	11
5.2.2	Secondary Endpoint	11
5.3	Subject Selection	11
5.3.1	Inclusion Criteria.....	12
5.3.2	Exclusion Criteria	12
5.3.3	Subject Withdrawal or Early Termination	13
5.4	Dosing.....	13
5.5	Study Timetable.....	14
6.1	Study Visit Summaries.....	14
6.2	Screening Visit.....	14
6.3	Baseline Visit.....	14
6.4	Follow-up Visits	15
6.5	Final Visit	15
7.1	Study Procedures.....	15
7.2	Data Collection	15
7.2.1	Vital Signs/Height and Weight	15
7.2.2	Laboratory Testing.....	15
7.2.3	Feasibility.....	16
7.2.4	Swelling/Inflammation.....	16
7.2.4.1	Endoscopy with Modified Patterson Scale.....	16
7.2.4.2	Cytokines	16
7.2.4.3	Digital Photography	16
7.2.5	Function	16
7.2.5.1	Neck Disability Index	16
7.2.5.2	Voice Handicap Index.....	17
7.2.5.3	Cervical and Shoulder ROM.....	17
7.2.5.4	Jaw ROM	17
7.2.6	Symptoms.....	17
7.2.6.1	Vanderbilt Head and Neck Symptom Survey (plus General Symptom Survey 2.0.....	17
7.2.6.2	Lymphedema Symptom Intensity and Distress Survey	17
7.2.7	Quality of Life.....	17
7.3	Study Device Application.....	17

	7.4 Study Schedule of Activities.....	18
8.0	Study Device Accountability	19
9.1	Risk Analysis and Adverse Events	19
	9.2 Risk Analysis.....	19
	9.3 Anticipated Adverse Events.....	19

2.0 Abbreviations

AE	Adverse Event
BP	Blood Pressure
CDT	Complete decongestive therapy
CFR	Code of Federal Regulations
CRF	Case Report Form
CTCAE	Common Terminology Criteria for Adverse Events
DVT	Deep vein thrombosis
FT	Flexitouch®
GSS	General Symptom Survey
HIPAA	Health Insurance Portability and Accountability Act
HNC	Head and neck cancer
HNL	Head and neck lymphedema
ICF	Informed consent form
ICH	International Council for Harmonisation
IRB	Institutional review board
L-SIDS	Lymphedema Symptom Intensity and Distress Survey
MLD	Manual lymph drainage
NDI	Neck Disability Index
REDCap	Research Electronic Data Capture
ROM	Range of motion
SD	Standard Deviation
VHI	Voice Handicap Index
VHNSS	Vanderbilt Head and Neck Symptom Survey

3.1 Introduction

3.2 Background and Rationale:

Secondary head and neck lymphedema (HNL) is a frequent side effect in patients treated for head and neck cancer (HNC) as the primary cancer or factors related to treatment (surgery, radiation, or chemotherapy) either destroy or obstruct lymphatic vessels and damage adjacent soft tissue.^{1,4} HNL occurs in over 90% of patients following HNC treatment.² HNL may involve external structures (soft tissues of the face, neck and eyes) or internal structures (oral cavity, mucous membranes, larynx and pharynx) but most often both are involved simultaneously.³ The resultant clinical impact is dependent on the anatomic sites involved and the extent of associated lymphatic dysfunction. Symptoms can range from mild to severe. The most common areas of external swelling and fibrosis are in the submental region and the neck.^{2,4} In severe cases, HNL may affect critical physical functions (e.g., respiration, mastication, swallowing, communication and vision). HNL, comparable to lymphedema at other sites, is often associated with psychological distress and degradation to quality of life.^{3,4}

In a recent study of 1,202 HNC patients, the majority of patients reported cosmetic concerns and discomfort. More than one third reported functional complaints, including difficulty swallowing (68%) and difficulty breathing (39%).² Internal swelling may be directly related to these symptoms. The most common functional complaint among patients who underwent total laryngectomy was difficulty breathing, often related to tracheostomal obstruction from submental edema.²

HNL patients often experience tightness and discomfort in the muscles of the neck and shoulders, which may impede range of motion and function of this muscular groups.³ Damage to the muscles in the affected region, may occur after radiation, resulting in atrophy, weakness and altered sensation.

Damaged lymphatics result in high-protein fluid collection in the affected tissues. Lymphedema is also associated with chronic inflammation, which may lead to a self-perpetuating and progressive course and exacerbation of symptoms.⁵ A study of filariasis disease, whose cardinal signs are lymphedema and massive fibrosis, found elevated TNF- α in early stages and determined that IL-6 and IL-8 were potential biomarkers for acute and chronic (highly fibrotic) stages of the disease.⁷ Pre-clinical models suggest cytokine driven pathways are involved in late-effect radiation-induced soft tissue damage and that persistent, elevated levels of some cytokines may foreshadow fibrosis after radiation.^{8,9,10} Even more relevant are results from, a descriptive, longitudinal study of 93 patients with head and neck cancer, conducted at Vanderbilt University, that followed lymphedema and fibrosis overtime, that found IFNg TNF- α , TGF- β , IL-1b, IL-6, MMP-2, MMP-9, and CRP were associated with lymphedema and fibrosis (confidential personal communication). Inflammation is clearly an area of concern for this patient population. One study (N=9), of individuals with chronic primary or secondary leg lymphedema, found that TNF- α significantly decreased after volume reduction treatment.¹⁰ Thus, manual therapy, may play a role in reduction of inflammatory cytokines and further exploration of such is warranted.

The standard treatment for HNL utilizes modified techniques of in-clinic complete decongestive therapy (CDT), including manual lymph drainage (MLD). Currently, some patients are able to continue simplified versions of these techniques at home, yet, many patients with HNL experience difficulty performing the treatment and/or find the treatment is insufficient in effectively managing their symptoms long-term. Clinicians and patients have therefore identified a need for additional effective options for at home treatment of HNL. In response, Tactile Medical™ has developed a garment for the treatment of HNL utilizing The Flexitouch® System pneumatic compression device (FT). Tactile Medical™ seeks to complete a study designed to evaluate the feasibility and potential effectiveness of the Flexitouch® on swelling/inflammation, symptom burden, and quality of life when used for lymphedema self-care.

3.3 Device Description :

Flexitouch® System (Tactile Medical™, Minneapolis, MN, USA): The Flexitouch® System is a segmental, calibrated, gradient pneumatic compression device that has been cleared for market in the US (K153311) (Appendix A), (US HCPCS code E0652) for the treatment of head and neck lymphedema. The device consists of a specifically designed garment set that covers the head, neck and chest and connects to an advanced pneumatic pump that includes programs specific for head and neck treatment. The Flexitouch® head and neck garment set is constructed of nylon and has up to 14 pneumatic chambers covering the head, neck and chest. The device applies brief applications of dynamic pressure in a wave-like manner to the treatment area. Used in conjunction with the Flexitouch® controller, the head and neck garment set is intended to treat lymphedema affecting the head and neck by stimulating the adjacent axillary lymphatic tributary regions and directing fluid from the affected area to healthy, functioning regions. (See Appendix A)

4.1 Study Objectives/Aims

4.2 **Objective:** The study will evaluate the feasibility, and preliminary effectiveness of the Flexitouch® head and neck treatment plus standard home care compared to standard home care regimen alone.

[figure not shown]
4.3 **Primary Aim:** To determine the feasibility of use of the Flexitouch® Head and Neck system, specifically a) to evaluate implementation fidelity (adherence) and barriers to implementation fidelity, b) to establish safety, and c) to assess satisfaction.

4.4 **Secondary Aim:** To determine the preliminary efficacy of Flexitouch® Head and Neck system compared to a wait-list control for the following outcomes: a) reduction in swelling/inflammation, b) function (cervical, jaw, and shoulder range of motion), c) symptoms, and d) quality of life.

5.1 Study Design

This study is an open label, multi-site, stratified by site, randomized, wait list control, pilot study. Vanderbilt University will serve as the multi-site coordinating center.

Within each study site:

5.2 Study Endpoints :

5.2.1 Primary Endpoints: The primary endpoint will occur when subjects complete the 8th week of treatment and provide: a) evaluation of implementation fidelity (adherence) and barriers to implementation fidelity, b) review of adverse events, and c) report satisfaction.

5.2.2 Secondary Endpoints: The secondary endpoints will be a) reduction in swelling/inflammation, b) function (range of motion cervical, jaw, and shoulder), c) symptoms, and d) quality of life.

5.3 Subject Selection

The study sample will be drawn from patients who have received head and neck cancer therapy and have developed HNL secondary to their cancer treatment.

Patients will be recruited from the head and neck cancer clinic at Vanderbilt University and similar clinics at the other investigational sites(s). The patient must have undergone (or attempted and failed) complete decongestive therapy (CDT), or is unable to access CDT as outlined in the inclusion criteria. Only patients who meet the criteria listed below will be considered for the study. A total sample of 40 subjects (20 per group balanced within each site) will be enrolled and those withdrawn for lack of adherence will be replaced, thus we may enroll up to 50 individuals.

5.3.1 Inclusion Criteria :

- Age \geq 18 years
- A previous diagnosis of histologically defined head and neck cancer
- A diagnosis of head and neck lymphedema
- Must be able and willing to participate in all aspects of the study and provide informed consent prior to study participation
- Complete cancer treatment with no evidence of active cancer; all post-surgical swelling must be resolved.
- The head and neck garments must fit appropriately. For patients with a tracheostomy, the fit will be assessed to ensure that the garments do not interfere with their tracheostomy.
- The subject must have experienced at least one of the following:
 - Completion of phase 1 lymphedema care in the past 8 weeks
 - The inability to participate/complete phase 1 care due to:
 - lack of available therapist/clinic
 - lack of insurance coverage or funding to support cost of care.

5.3.2 Exclusion Criteria: Subjects will be determined to be ineligible for this study if they meet any of the criteria described below :

- Uncontrolled hyperthyroidism or parathyroidism (for which endocrinologist recommends against neck compression)
- Carotid sinus hypersensitivity syndrome
- Symptomatic carotid artery disease, as manifested by a recent transient ischemic attack (within 30 days), ischemic stroke, or amaurosis fugax (monocular visual ischemic symptoms or blindness)
- Symptomatic bradycardia in the absence of a pacemaker
- Internal jugular venous thrombosis, acute or within 3 months
- Increased intracranial pressure or other contraindications to internal or external jugular venous compression
- Acute radiation dermatitis, unhealed surgical scar, unhealed or open wound(s), surgical flap less than 6-8 week post-operative
- Facial or head and neck dermal metastasis
- Acute facial infection (e.g., facial or parotid gland abscess)
- Any condition in which increased venous and lymphatic return is undesirable
- History of pulmonary edema or decompensated congestive heart failure with in six (6) week of enrollment.
- Subject is pregnant or trying to become pregnant

5.3.3 Subject Withdrawal or Early Termination:

Subjects will exit the study if they meet any of the following criteria:

- Subject death
- Subject voluntarily withdraws
- Subject experiences a serious adverse event that in the investigator's clinical judgment necessitates study discontinuation
- Subject acquires any of the exclusion criteria, except
 - In the case of a subject acquiring an infection, they may remain in the study per the discretion of the investigator. Detailed information regarding the infection, nature, treatment, and duration, will be recorded.
- Non-adherence with any study procedures as defined by no use of device during a consecutive 7-day period as documented on the diary or failure to complete required documents.

5.4 Dosage:

Wait-list Control Group: Subjects will continue their home care regimen as defined by their physician/healthcare provider. The home care regimen may include:

- self-MLD
- exercise
- skin care
- wearing an appropriate compression garment.

After 8 weeks, the subject will then receive treatment as outlined below in the investigational group if they so desire.

Investigational Group: Subjects in the investigational group will use the Flexitouch® pneumatic compression device in addition to the home care regimen defined by their treating physician/healthcare provider. The subject will complete two treatment sessions daily using the Flexitouch® head and neck system for the full 8 weeks of study participation. The twice daily treatment will include the H1 program for the head, neck and chest with an approximate 25-43 minute single cycle time as outlined in the Flexitouch® System User Guide (Appendix A). Instructions for the application of the head and neck garments are located in Chapter 6 of the Flexitouch® System User Guide (Appendix A). The home care regimen may include:

- self-MLD
- exercise
- skin care
- wearing an appropriate compression garment, if applicable

5.5 Study Timetable:

	1- 3months	4-6 months	7-9 months	10-14 months
IRB Review	X			
Enrollment	X	X	X	
Treatment		X	X	
Data Entry		X	X	
Data Analysis			X	
Manuscript Draft			X	
Publication				X

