6.1 Study Visit Summaries

6.2 Screening:

The subject will provide written informed consent prior to screening. The study will be explained to each subject. An Informed Consent Form (ICF) will be signed by each subject before study participation as mandated by FDA regulations and the institutional review board (IRB). (See Appendix B) A blank copy of the IRB approved informed consent form must be kept on-site and by Tactile Medical™. A copy of the ICF will be given to the subject to read and take home to consider, if they prefer. All the subject's questions must be answered prior to signing the ICF. Research procedures cannot be performed until the subject provides consent. The signed original for each subject must be kept in the subject's research records. A copy of the signed consent form will be given to each subject.

After informed consent is obtained, screening will commence. (See Appendix C: Screening Form) The subject's head and neck measurements will be taken to assist with garment size selection. For subjects with a tracheostomy, the fit will be accessed further to ensure that the garments do not interfere with their tracheostomy. The head and neck garment measuring guide is included in Appendix A. Should the head and neck measurements indicate the garment will not fit, no further information will be obtained and the subject will be withdrawn. After the garment fit has been confirmed the remaining inclusion and exclusion criteria will be evaluated to ensure that the subject meets all entrance criteria. The subject should not undergo any study specific procedures until after the informed consent process and screening processes are complete.

6.3 Baseline Visit:

The screening and baseline visit can occur on the same day or different days depending on the needs of the subject. At this visit, the subject will undergo the baseline data collection procedures as outlined in the Study Schedule of Activities in section 7.4.

Randomization:

After completing the informed consent process and baseline data collection (including the endoscopy) subjects enrolled at each site will be randomized (1:1) to either the investigational group or wait-list control group via the use of a computer-generated, permuted block program executed by the study biostatistician. Each site will have its own unique randomization list.

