Subjects randomized to the investigational group at each site will follow the Study Schedule of Activities table in section 7.4 and will complete the study in 8 weeks. The subjects that are randomized to the waitlist group at each site will complete all study activities as outlined below in table 7.4. After completing the 8 weeks of the standard regimen, the subjects may choose to receive the same treatment as was implemented in the investigational group. No study data will be completed; however, patients opting to use the device will be seen at weeks 9, 12, and 16 for a documented safety check as outlined in section 7.4.

Research team members will provide the subjects with a self-care kit and provide instructions on how to use the kit. All subjects will leave the initial baseline visit with the self-care kit (Appendices D & E) that includes:

- Subject Diary (intervention group only)
- Self-care checklist
- Dates and Times for their upcoming appointments
- Contact information and instructions to call if any questions

6.4 Follow Up Visit(s):

The subject follow up visits will occur at 1 and 4 weeks (± 3 days). The study staff will collect the checklist and review the subject diary with the intervention patients during each visit to ensure that all entries are complete and understood by the study staff. Any corrections must be made by the subject, and initialed and dated by them. At the visit, the subject will undergo the study procedures as outlined in the Study Schedule of Activities in section 7.4.

6.5 Final Visit:

The final study visit will occur at 8 weeks (± 3 days). At this visit, the subject will undergo the study procedures as outlined in the Study Schedule of Activities in section 7.4. The study staff will collect the checklist and review the subject diary with the subject during each visit to ensure that all entries are complete and understood by the study staff. Any corrections must be made by the subject, and initialed and dated by them.

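### Non-users of the device exit and are replaced although adherence and satisfaction are primary, and the plan does not say whether they count in those two percentages

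*Combined protocol and SAP*

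**What the plan says.** The primary aim (section 4.3) is feasibility, and its first element is "to evaluate implementation fidelity (adherence) and barriers to implementation fidelity"; safety and satisfaction follow. Section 5.2.1 places the primary endpoint at completion of week 8.

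Section 5.3.3 lists the reasons for leaving the study. One is "Non-adherence with any study procedures as defined by no use of device during a consecutive 7-day period as documented on the diary"; the same item adds "failure to complete required documents". Section 5.3 then states that "those withdrawn for lack of adherence will be replaced, thus we may enroll up to 50 individuals". The Synopsis (Number Planned) is wider: "40 subjects randomized with replacement of up to 10 early withdrawals".

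Under section 5.4, "The subject will complete two treatment sessions daily" for the full 8 weeks. Only the intervention group keeps a diary (section 6.3), and staff review it at weeks 1, 4 and 8 (sections 6.4 and 6.5). In section 7.4 the post-treatment survey appears only at week 8 and only for the intervention group. Endoscopy and cytokines appear only at baseline and week 8.

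Section 12.4 summarises adherence, barriers, adverse effects and satisfaction as percentages and compares rates by group with likelihood chi-square tests. It expects at least 75% of all enrolled to complete, and 80% of the investigational group to rate satisfaction above neutral at the end of the study. Section 12.3 treats non-random missing visits as informative and rules out imputation. No analysis set is defined.

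**The concern.** People who stop using a twice-daily home device are the most direct evidence on whether it is feasible. Under the exit rule they leave before the week-8 survey, and someone else is enrolled in their place. Completion has a stated denominator, all enrolled. Adherence has none, and satisfaction has only a reference to the investigational group at the end of the study. Nothing says whether exited users count, or how the sessions after their exit count.

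The non-use criterion is read from the diary, so during the 8 weeks it can act only on the device arm. The incomplete-documents criterion can act on either arm.

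At stake are two of the study's main results. Both could be reported among finishers, where they would look better than among everyone given the device. Satisfaction has an explicit target that such reporting could help it meet.

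**Working it through.** **Inputs from the protocol.** Two sessions a day for 8 weeks (5.4); exit after 7 days of non-use (5.3.3); 20 per group, at most 10 replacements, up to 50 enrolled (Synopsis, 5.3); targets of 80% for satisfaction and 75% for completion (12.4).

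**Assumptions.** The number, arm and timing of exits; 80% of finishers above neutral; finishers averaging 80% adherence. The documents give none of these.

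**The plan's own figure.** Section 12.4 states 80% power with 20 completers per group for 0.9 SD, two-sided alpha 0.05. Normal approximation: Φ(0.9 × √(20/2) − 1.96) = Φ(0.886) = 81.2%. The two-sample t-test gives 79.2%. The figure reproduces. It rests on completers, so keeping exited users in the data does not alter it.

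**Which arm replacements join.** Section 5.3 wants 20 per group balanced within each site. Section 6.3 has participants "randomized (1:1) to either the investigational group or wait-list control group via the use of a computer-generated, permuted block program". No rule says which arm a replacement joins. Replacing 5 or 10 device exits within the arm gives 25 or 30 device starters and 20 finishers. Filling all 50 places at 1:1 gives 25 starters per arm, and 10 device exits then leave 15 finishers.

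**Satisfaction, exited users counted as not satisfied (lower bound).**
- Finishers only: 16/20 = 80%, target just met.
- 1 exit: 16/21 = 76%, target missed.
- 5 exits, 25 starters: 16/25 = 64%.
- 10 exits, 30 starters: 16/30 = 53%.
- 10 exits, 25 starters: 12/15 = 80% of finishers becomes 12/25 = 48%.

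If every exited user were satisfied, the figures would be 17/21 = 81%, 21/25 = 84%, 26/30 = 87% and 22/25 = 88%. The true value lies between the two bounds and cannot be known unless these people are surveyed.

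**Adherence, one user.** Scheduled sessions: 2 × 56 = 112. A user who does every session for 14 days, then none, and exits at day 21 has 28/42 = 67% to exit and 28/112 = 25% of the schedule, or is absent if only finishers are summarised.

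**Adherence, group mean (finishers at 80%, exits as above).**
- 5 exits, 25 starters: to exit (20 × 0.80 + 5 × 0.667)/25 = 77%; all scheduled sessions (20 × 0.80 + 5 × 0.25)/25 = 69%.
- 10 exits, 30 starters: to exit (20 × 0.80 + 10 × 0.667)/30 = 76%; all scheduled (20 × 0.80 + 10 × 0.25)/30 = 62%.
- 10 exits, 25 starters: all scheduled (15 × 0.80 + 10 × 0.25)/25 = 58%.

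Range if use stops after day 7 (14/112 = 12.5%) or day 28 (56/112 = 50%): 67% to 74% for 5 exits with 25 starters; (16 + 1.25)/30 = 58% to (16 + 5)/30 = 70% for 10 exits with 30 starters.

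**Completion.** With 10 device-arm exits and no others, pooled completion is 40/50 = 80%, which meets the 75% target. Device-arm completion is 20/30 = 67% with within-arm replacement, or 15/25 = 60% without. In the second case the likelihood chi-square for 15/25 against 25/25 is 2 × (15 ln 0.75 + 10 ln 2 + 25 ln 1.25) = 16.39, p < 0.001.

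**The case against.** The strongest reply is that the plan already exposes much of this. The completion target counts everyone enrolled, so withdrawals lower it. Rates are to be compared by group, and the calculation above shows that such a test would reveal a lopsided loss if it is applied to completion. Missing visits are called informative. Diaries are reviewed at weeks 1 and 4, so adherence before exit is not lost by design. All of this stands, and it narrows the concern to adherence and satisfaction. It does not supply their denominators, and the completion target remains pooled.

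A second reply is that week-8 respondents are the natural reading, so one sentence would settle the matter. The reading is plausible, but it is nowhere stated, and it is the reading that leaves out the people who stopped. Section 7.2.3.3 times the survey at the end of the intervention, which could allow one at exit; the schedule provides none. Appendix E, the feasibility forms, was not in the text reviewed.

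Third, replacement has a purpose: it serves the 20 completers per group behind the stated power. That is fair, and replacement can stay. Keeping exited users in the data does not conflict with it.

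Fourth, scoring every session after any exit as missed would count deaths and safety exits as non-adherence. That is right, and the fix separates them.

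**Conclusion.** The concern holds for adherence and satisfaction. Followed as written, the exit rule and the week-8 schedule tilt satisfaction towards finishers, and adherence can be computed in several ways with materially different answers. In the illustration, satisfaction of 80% among finishers has a lower bound of 76% with one exit and of 64% or 53% with five or ten replaced within the arm. Adherence of 80% among finishers becomes 69% or 62% over all scheduled sessions, and 58% if 15 of 25 starters finish. These sizes rest on assumed exit counts, assumed stopping times and assumed finisher results; only the cap of 10 replacements comes from the documents.

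A reader might infer three stronger things that the text does not support:
- That the plan hides dropout. It does not: completion is measured over all enrolled and by-group comparisons are planned.
- That the plan prescribes a finishers-only analysis. The week-8 wording suggests one, but no rule states it.
- That the efficacy comparison is biased by a known amount. That would depend on how non-use relates to outcome, which the documents do not give, and efficacy is a secondary aim.

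This should be fixed, because feasibility is the primary aim and the change is small.

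**What to change.** 1. In 5.3.3, for exits due only to device non-use or incomplete documents, separate these from exit from data collection. Record them as adherence outcomes. With continued consent, keep the assessments already planned (endoscopy at the investigator's judgment) and, for device users, the post-treatment survey. Leave the other exit criteria unchanged.
2. In 12.4, report adherence for all randomised to the device, counting sessions after a non-use exit as not done. Report exits for death, serious adverse events or acquired exclusion criteria separately, with adherence to exit, so that safety exits are not scored as non-adherence.
3. Report satisfaction among responders, beside the lower bound over all randomised to the device. The no-imputation rule then stands for the main summary.
4. Report completion by arm beside the pooled 75% target.
5. State that replaced participants stay in the analysis set, and that Aim 2 is analysed as randomised with all available data.
6. Reconcile the Synopsis and section 5.3 on who is replaced.

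The cost is protocol and analysis-plan wording, plus already planned visits for perhaps 10 people. The downside is visit burden for people who have stopped using the device, including a blood draw and, where the investigator agrees, an endoscopy with the risks listed in section 9.3. The feasibility percentages are also likely to look less favourable.
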